Based on previous studies in rat models using a plasmid DNA vaccine encoding PAP, we conducted a phase I/II trial in patients with high-risk stage D0 prostate cancer using this same DNA vaccine (pTVG-HP). No significant adverse events were observed in 22 subjects treated over a 12-week period of time. Moreover, several patients developed evidence of PAP-specific CD8+ T-cells, and several patients experienced a prolongation in the PSA doubling time, demonstrating immunological efficacy and possible clinical efficacy [15]. IFN $\gamma$ -secreting immune responses to PAP detectable at multiple times months after immunization were detectable in individuals with evidence of prolonged PSA doubling time [16]. A second trial was conducted in patients with castration-resistant, non-metastatic prostate cancer (clinical stage D0.5/M0) that evaluated treatment over a 2-year period of time and with different schedules of administration. That trial similarly demonstrated safety, and the induction of durable Th1-biased immune responses specific for the PAP target antigen [17]. These findings have justified further evaluation of this vaccine in a randomized phase II clinical trial (NCT01341652), evaluating whether vaccination with pTVG-HP versus placebo increases the 2-year metastasis-free survival of patients with high-risk PSA-recurrent, non-metastatic prostate cancer (stage D0) at high-risk for metastatic progression as defined by a PSA doubling time of less than 12 months. That trial has completed accrual, and is expected to be completed in 2018.

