In the setting of PSA recurrence after definitive therapy, this stage D0/M0 being evaluated, it is assumed that patients have metastatic disease that is simply below the level of current methods of detection. We and others have demonstrated that NaF PET/CT provides a more sensitive method of detecting bone metastases in patients with more advanced prostate cancer {Morisson, 2013 #4088}, suggesting that this method may be more sensitive in detecting minimal residual disease in the setting of PSA recurrence. Moreover, NaF PET/CT can provide a more

quantitative assessment of total bone involvement, an assessment that cannot be determined from standard bone scintigraphy {Morisson, 2013 #4088}, when combined with advanced image analysis, such as in Quantitative Total Bone Imaging (QTBI), developed at University of Wisconsin Carbone Cancer Center. QTBI can be used to evaluate changes in total prostate cancer bone involvement over time, effectively a measure of tumor growth rate in bone. Our group explored the role of NaF PET/CT in a similar patient cohort in a subset of patients enrolled in a randomized phase II trial of pTVG-HP versus GM-CSF adjuvant in patients with non-metastatic prostate cancer (NCT01341652). Among 34 patients who had NaF PET/CT scans, only 4 of 34 did not have a lesion identified at baseline, and only 1 of 34 patients had no lesions at any time point. Although the median number of lesions detected and change in total activity ( $SUV_{total}$ ) was not significantly different for the two treatment cohorts, the median  $SUV_{total}$  increased 50.4% in the GM-CSF arm and decreased 23.0% in the pTVG-HP arm [manuscript under preparation].

In this study we wish to further explore, whether these methods could be used to identify individuals at particularly high risk for early disease progression and to evaluate whether treatment with a DNA vaccine in combination with nivolumab can affect the tumor growth rate analogous to changes in PSA doubling time. Moreover, we wish to determine whether the pattern of disease progression (continued growth of all lesions, or rapid growth of individual lesions) differs among patients based on their response to treatment.

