### 5. Patient Selection

#### A. Inclusion Criteria

1. Patients must be at least 18 years of age with a histologic diagnosis of adenocarcinoma of the prostate
2. Patients must have undergone radical prostatectomy
3. Patients must have completed local therapy by surgery and any adjuvant/salvage radiation therapy at least 3 months prior to entry, with removal or ablation of all visible disease, including seminal vesical and/or local lymph node involvement.

4. Patients must have biochemically recurrent, non-metastatic (by CT and bone scan) clinical stage D0/M0 disease defined by the following:
  - Patients must have evidence of detectable serum PSA with at least 4 serum PSA measurements available, from the same clinical laboratory, at least two weeks apart up to one year, and the final serum PSA value must be  $\geq 2.0$  ng/mL.
  - PSA doubling time, calculated from most recent 4 serum PSA values (collected up to one year prior to enrollment, at least 2 weeks apart, and all from the same clinical laboratory), must be a positive number (i.e. evidence of PSA rise over time).
  - PSA doubling time will be calculated using the Memorial Sloan-Kettering Cancer Center nomogram:  
(<http://www.mskcc.org/applications/nomograms/prostate/PsaDoublingTime.aspx>).
  - Patients must not have definitive evidence of metastases as determined by CT of the abdomen/pelvis and bone scintigraphy (bone scan). Note: patients with lesions detectable by highly sensitive methods (e.g. NaF PET imaging or PSMA PET imaging) will be considered eligible as long as these lesions do not meet size criteria on CT imaging (visceral lesions suspicious for metastases or lymph node  $> 15$  mm in short axis) and/or are not independently observed on bone scan.
5. Patients with a prior history of a second malignancy are eligible provided they have been treated with curative intent and have been free of disease greater than three years. There will be no exclusion for patients with a history of basal cell carcinoma, squamous cell skin cancer, superficial bladder cancer, or other *in situ* carcinoma that has been adequately treated.
6. Patients who are sexually active must use a reliable form of contraception while on study and for 4 weeks after the last immunization.
7. ECOG performance score  $< 2$  and life expectancy of at least 12 months.

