#### D. Quantitative Total Bone Imaging (QTBI) using NaF PET/CT

An assessment of small volume bone metastatic disease (potentially not detected by standard bone scintigraphy) and tumor growth rates will be conducted using QTBI. Patients selected to participate in the NaF PET/CT part of the study will be assessed at baseline, week 12, and week 24 by NaF PET/CT. Metastatic prostate cancer lesions in bone will first be localized and identified based on functional NaF PET uptake, assisted with the anatomical information

provided by CT scans. Segmentation will be performed using an automatic segmentation method (e.g. a fixed SUV threshold), and adjusted with physician guidance. Scans from different time points will be registered to one another using an articulated registration technique employing a rigid registration of skeletal elements (bones) from CT followed by registration optimization by combining with deformable registration of bones and lesions from NaF PET/CT. The lesions between pre-treatment and follow-up scans will be matched to establish longitudinal correspondence of the lesions. For each patient, comprehensive treatment response metrics will be calculated, consisting of SUVtotal (total disease burden), SUVmax (maximum intensity lesion), SUVmean (average intensity), the number of lesions, and total volume of bone lesions. In addition, imaging response metrics will be calculated for each individual lesion. This methodology will specifically be used to assess the growth rate of bone metastatic disease by evaluating changes from baseline to month 3 and from month 3 to month 6. In terms of logistics, each of the clinical centers has the capacity and expertise to perform NaF PET imaging.

NaF-PET/CT IMAGING PROCEDURES: To ensure uniformity as well as optimal data interpretation, a standardized image acquisition protocol will be utilized and the overall imaging analyses will be conducted centrally under the supervision of [name], PhD (co-investigator) at the University of Wisconsin Image Analysis Core (IMAC) facility, with all analysis blinded to study treatment arm. Please refer to the Standard Operating Procedures (SOP) document for NaF-PET/CT procedures, which will be adhered to at both sites, for details of image acquisition, image analysis, image interpretation, image submission for central review, and other imaging-related details.

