### (4) Exploratory Objectives

The number of antigen-specific T-cell and/or IgG responses will be summarized in terms of means, standard deviations, medians and ranges for each assessment time point. Changes from baseline will be evaluated using a nonparametric Wilcoxon Signed Rank test. A negative binomial or overdispersed Poisson model (depending on the model fit) will be utilized to evaluate whether antigen-specific T-cell and/or IgG responses are elicited with treatment. Univariate and multivariate logistic regression analysis will be conducted to examine whether the development of PAP-specific T-cell immune responses and antigen spread are associated with PSA response.

**Results from the QTBI analysis will be used to determine (1)** whether QTBI by NaF PET/CT can identify bone lesions in this patient population not detected by standard bone scintigraphy, (2) whether the presence of lesions detected by NaF PET/CT at baseline is associated with early disease progression (within 1 year) by standard radiographic imaging methods (CT and bone scintigraphy), and (3) whether growth rates, and changes in growth rates, determined by NaF PET/CT are associated with PSA doubling time and changes in PSA doubling time. Sensitivity of QTBI by NaF PET/CT to identify bone lesions will be summarized in tabular format and compared to sensitivity of standard bone scintigraphy using a paired McNemar's test. Univariate and multivariate Cox proportional hazard regression analyses will be conducted to evaluate the associations between presence of lesions detected by NaF PET/CT at baseline and time to disease progression. Analogously, univariate and multivariate logistic regression analyses will be performed to evaluate the associations between presence of lesions detected by NaF PET/CT at baseline and 1-year PFS rate. The associations between changes in QTBI parameters (SUVmax, SUVmean, SUVtotal) and changes in PSA doubling time will be evaluated using linear mixed effects modeling with subject specific random effects.

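### Any-lesion presence on baseline NaF PET/CT is a weak sole predictor of progression when about 88% of patients may have a lesion; a burden measure already being calculated would serve better

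*Combined protocol and SAP*

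**What the plan says.** Exploratory objective 5 (Synopsis, Section 3 and Section 10.B) asks whether having lesions on the baseline NaF PET/CT is associated with radiographic progression within a year. Section 10.D(4) gives the analysis: univariate and multivariate Cox models to "evaluate the associations between presence of lesions detected by NaF PET/CT at baseline and time to disease progression", and logistic models for "presence of lesions detected by NaF PET/CT at baseline and 1-year PFS rate". The predictor is binary in both. No threshold, alternative coding, sparse-data method or power statement is given.

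Section 2.F supplies the only prevalence figure: "Among 34 patients who had NaF PET/CT scans, only 4 of 34 did not have a lesion identified at baseline". It introduces that experience with the words "Our group explored the role of NaF PET/CT in a similar patient cohort".

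Section 9.D says that for each patient "comprehensive treatment response metrics will be calculated", naming SUVtotal, SUVmax, SUVmean, lesion number and total lesion volume. Section 10.D(4) relates the SUV parameters to PSA doubling time only, not to progression.

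**The concern.** A predictor that takes the same value in nearly everyone has little contrast to offer. If about seven in eight patients have a lesion, the comparison group is a handful of men, and with few progression events it may contain none. The odds ratio then has no finite maximum likelihood estimate, and the Cox hazard ratio is unstable or infinite. Adjusting for further covariates makes this worse.

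At stake is whether objective 5 gives a usable answer. Section 2.F wants NaF imaging to pick out men at particularly high risk of early progression. A marker positive in most of the cohort cannot isolate a high-risk minority, and a null from such a comparison would say little in either direction.

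**Working it through.** The plan states no power or event count for this analysis, so there is no figure of its own to reproduce.

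**Inputs from the protocol**
- Lesion-free share: 4/34 = 11.8%, exact 95% CI 3.3% to 27.5% (Section 2.F).
- Maximum sample size: 41, or 21 if the trial stops after stage 1 (Section 10.C).
- Background metastasis rate: median 8 years (Section 1). If exponential, 1 − 0.5^(1/8) = 8% at one year and 1 − 0.5^(2/8) = 16% at two years, so about 3 and 6 to 7 events in 41.

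**Assumptions, not in the protocol:** hazard ratios, odds ratios, one-year rates above 8%, and a two-sided 5% level.

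**1. Lesion-free patients.** 41 × 4/34 = 4.8. With 11.8% taken as known, the binomial 95% range is 1 to 9. Over the confidence limits for 4/34, the expected number runs from 41 × 0.033 = 1.4 to 41 × 0.2745 = 11.3. At 21 patients it is 21 × 4/34 = 2.5.

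**2. One-year comparison, 5 versus 36** (exact Fisher power, standing in for univariate logistic regression).
- 10% versus 40% progression: 2.5%.
- 5% versus 30%: 0.1%.
- With 0 of 5 events among the lesion-free, 20 of 36 (56%) of the others must progress within a year to reach p ≤ 0.05.
- At a true 10% rate, the chance of no events among 5 is 0.9^5 = 59%.

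**3. Simulation, 41 patients.** Burden is standard normal, log-odds of one-year progression are linear in it (odds ratio 2 to 3 per SD), and presence is the same score cut so that 4/34 are negative. The binary predictor is tested by Fisher and the continuous one by Mann-Whitney. Ranges run from odds ratio 2 to 3 and are rounded; repeat runs differ by a point or two.

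| Assumed one-year rate | Zero cell | Power, binary | Power, continuous |
|---|---|---|---|
| 8% | 90% to 96% | below 0.1% | 17% to 35% |
| 15% | 80% to 91% | below 0.1% | 27% to 54% |
| 30% | 58% to 76% | 2% to 4% | 45% to 76% |

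**4. Cox model.** Schoenfeld's formula with q = 4/34, so q(1 − q) = 0.104.
- Events for 80% power = (1.96 + 0.84)² / [0.104 × (ln HR)²]: 158 at HR 2, 63 at HR 3, 40 at HR 4, against at most 41 patients.
- Power with d events = Φ(√(0.104 d) × ln HR − 1.96). For d = 4 to 12: 7% to 12% at HR 2, 11% to 23% at HR 3, 14% to 34% at HR 4.
- The formula is generous with so small a group. A simulated log-rank test with 5 versus 36 gives at most 1.4% when 20% to 30% of lesion-positive patients progress by two years, and 7% to 13% when 50% do (HR 2 to 4).

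**The case against.** **The prevalence may not transfer.** The 34 men came from a trial in high-risk disease, "as defined by a PSA doubling time of less than 12 months"; Section 5.A here asks only for a positive doubling time. More lesion-free men are therefore possible. This stands as a caution, but 10 lesion-free versus 31 still gives Fisher power of only about 32% for 10% versus 40%. In the other direction, Section 9.D speaks of patients selected for NaF imaging and the week 12 and 24 scans are limited to designated sites (Section 8), so fewer than 41 may be scanned.

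**Few events are much of the problem, and recoding cannot cure that.** This stands. At an 8% one-year rate even the continuous measure has only 17% to 35% power. A reader might take the 45% to 76% at a 30% rate as the expected gain, but the protocol gives no such rate.

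**The simulation favours the continuous measure by construction.** Also true. Presence is a cut of the same score, and nothing in the protocol shows a dose-response with SUVtotal. If risk differs mainly between men with and without lesions, the advantage shrinks.

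**The analysis is exploratory, with no power claimed.** Correct, and it limits the weight of the point. But an exploratory model should still be estimable, and Section 10.D(1) promises a detailed SAP in which this can be settled.

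**Conclusion.** The point holds as a weakness in the choice of predictor. If the prevalence in Section 2.F carries over and all 41 patients are enrolled and scanned, about 5 will be lesion-free. The one-year logistic model will then probably have a zero cell (about 60% to 95%), with binary power of about 0% to 4% in the simulations, and the Cox model will have low power (about 7% to 34% over the range shown). These figures rest on assumed effect sizes and event rates and on 4/34, which is itself imprecise.

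A reader might infer that the Cox analysis has virtually no power whatever happens, or that objective 5 is unanswerable. The documents do not support that. They give no event rate for this cohort, and in an extreme case (all 41 progressing, HR 4) Schoenfeld power would be 82%. Nor do they show that a null would be reported as absence of association; the risk is that nothing in the plan warns against that reading. No primary endpoint, stopping rule or treatment decision depends on this analysis.

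**What to change.** In Section 10.D(4), pre-specify one baseline burden measure from Section 9.D as the main predictor in the univariate Cox and 1-year models. Lesion count would do, as would log(SUVtotal + c) with the constant c stated in advance. The constant matters because log(SUVtotal) is undefined for a man with no lesions, and dropping such men would remove the low end of the scale.

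Keep any-lesion presence as a descriptive report: progression by presence, with exact intervals, and a sentence saying that a null for presence is not evidence of no association. State the number scanned and the number of events beside every estimate.

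The cost is small. No new scans or data are needed. Objective 5 is worded around presence in the Synopsis, Section 3 and Section 10.B, so it needs a matching edit, submitted as an amendment under Section 14.D. Precision may still be limited by few events, and the plan should say so.

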## **11. Administrative Considerations**

### **A. Specimen Handling**

Upon entry into the study, each subject will be assigned a unique identification number. All materials collected on that subject will be labeled with that number only, for reasons of confidentiality. Lymphocytes collected will be stored in liquid nitrogen, and sera will be aliquoted and stored at -80°C in research laboratories at the investigator sites, and shipped in bulk to the central UWCCC laboratory for immune analysis.

### **B. Future Use of Samples**

Not all of the blood components obtained during this study may be required for the tests that are part of the clinical trial. Following the conclusion of the study, the samples may be used for future cancer research at University of Wisconsin or other sites. This research will help to understand disease subtypes, drug response and toxicity, and possibly identify new drug targets or biomarkers that predict subject response to treatment. Patients will be given the option to opt out of the sample banking process.

Samples will be coded with the subject's unique study identification number and date sample was drawn, which can be linked back to individually identifiable information. The link between the unique subject identification number and the identifiable information will be stored in a secure location in a password protected computer, with only appropriately trained staff having access to this link. Samples will be stored in the research laboratory of the University of Wisconsin Carbone Cancer Center in Madison, Wisconsin. This is a secure facility and only appropriate people will have access to the blood samples.

### **C. Institutional Review Board**

In accordance with federal regulations (21 CFR 312.66), an Institutional Review Board (IRB) that complies with the regulations in 21 CFR 56 must review and approve this protocol and the informed consent form prior to the initiation of the study at each investigator site. In addition, the study cannot be instituted without FDA approval of the vaccine formulations. Finally, the trial will be conducted with adherence to this protocol, following good clinical practice (GCP) guidelines, and in compliance with other applicable regulatory requirements. Any modifications to the protocol must follow the procedure as outlined in Section 17 below.

As the Coordinating Center for a trial, it is UWCCC's responsibility for oversight of regulatory documentation for each participating site including verifying that the participating has an IRB and a Federal wide assurance to cover its activities. After UW Health Sciences Institutional Review Board (HS-IRB) grants initial approval, the UWCCC GU Oncology Group staff will provide the approved protocol, and consent form to the participating site. The participating site will use the UW HS-IRB approved consent document as a template. No substantial changes, including changes to the risk language will be allowed without first receiving approval from the UWCCC GU Oncology Group.

Each participating site must receive local IRB approval of both the current protocol and consent prior to activation of the study at their site. The local IRB approval notice, approved HIPAA and consent will be forwarded to the UWCCC GU Oncology Group at the contact listed below either by mail, fax or email. Once all of the UWCCC administrative requirements are completed, the UWCCC GU Oncology Group will issue an activation notice for the site and subjects can be enrolled into the study:

In addition, the participating institution must provide the UWCCC GU Oncology Group with a copy of the institution's approved continuing review. Registration will be halted at the participating institution if a current continuing review approval is not on file at UWCCC.

All local IRB approvals and informed consent documents should be forwarded to the UWCCC GU Oncology Group by email at [[contact]](mailto:[contact]) or fax at [contact] or regular mail at:

UWCCC GU Oncology Group  
University of Wisconsin Carbone Cancer Center  
[name]  
[name]

#### D. Consent

The Principal Investigator or their associates must explain verbally and in writing the nature, duration, and purpose of the study and possible consequences of the treatment. Patients must also be informed that they may withdraw from the study at any time and for any reason without jeopardizing their future treatment. In accordance with Federal regulations (21 CFR 312), all patients must sign the IRB-approved consent form.

Documentation of both the informed consent process and that the process occurred prior to a subject's entry into the study should be recorded in the subject's source documents. The original

consent form, signed and dated by the subject and by the person consenting the subject prior to the subject's entry into the study, must be maintained in the investigator's study files at each site.

## **12. Data and Safety Monitoring Plan**

### **A. Definitions**

Adverse events (AE) are defined as any unfavorable and unintended sign (including abnormal laboratory finding), symptom or disease temporally associated with a medical treatment or procedure, regardless of whether it is considered related to the treatment or procedure. Adverse events are categorized as definite, probable, possible, unlikely or unrelated in relation to the medical treatment or procedure performed.

